# 11.0 Data Review

# 11.1 Data Handling and Transfer

PRA will provide data handling and transfer in accordance with Data Management Plan and Data Transfer Plan both dated 12Nov2018.

# 11.2 Data Screening

Beyond the data screening built into the PRA Data Management Plan, the PRA programming of analysis datasets, tables, figures, and listings (TFL) provides additional data screening. Presumed data issues will be output into SAS logs identified by the word "Problem" and extracted from the logs by a SAS macro and sent to Data Management.

Reviews of a pre-lock TFL run (if included in the study contract) allow for further data screening prior to lock. The PRA statistician and the sponsor must approve database lock.

# 12.0 Statistical Methods

Data analyses will primarily be descriptive. The purpose of this study is to identify a ganaxolone dose and exposure level that is safe and well tolerated. Efficacy data will be collected but will be considered hypothesis-generating; i.e., there are no *a priori* hypotheses on which the study was powered. Results from exploratory statistical analyses may be presented but only to aid in interpretation.

Unless otherwise indicated, continuous variables will be summarized with the following descriptive statistics: n (number of observations), (arithmetic) mean, standard deviation (SD), first and third quartiles (Q1 and Q3), minimum (min) value, median, and maximum (max) value. The minimum and maximum values will be displayed to the same level of precision as the raw data, the median and mean to a further decimal place and the SD to two additional decimal places – up to 4 decimal places total.

Categorical data will be summarized with frequencies and percentages. Percentages by categories will be based on the number of subjects exposed within a treatment. Percentages will be rounded to one decimal place.

All analyses will use SAS version 9.4 or higher. Tables will present data summarized by treatment group within cohort. For each summary table, corresponding supportive listing(s) will be provided.

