## 9.5.8.3 Exploratory Endpoints

# 9.5.8.4 Statistical Methods

Observed values and changes from baseline for HAMD17, EPDS, and STAI6 total scores, subscales, and individual items will be summarized by visit. The categorical outcomes of HAMD17 response, HAMD17 remission, and CGI-I will be summarized by visit.

The preferred approach for exploratory analysis of continuous efficacy variables will be mixed model repeated measures (MMRM) but other approaches such as t-tests, analysis of covariance, or non-parametric methods may be used if necessary or more practical. Similarly, the preferred approach for analysis of categorical efficacy variables will be repeated measures (e.g., generalized estimating equations) but other approaches such as chi square or Fisher's exact tests may be used.

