For efficacy endpoints expressed as categorical (including binary) variables, summary tables will show frequencies and percentages of subjects in each category as well as adjusted event rates with SEs and associated p-values using general estimating equations (GEE). Summary statistics by time point will also be displayed graphically using bar charts. GEE models will include main effects for treatment and visit and an interaction term for treatment-by-visit. Baseline will be included as a covariate where applicable. Unstructured covariance will be specified but alternative structures (e.g., CS) or alternative statistical methods (e.g., chi square tests of association) may be used if GEE convergence cannot be achieved. GEE assumes missing observations are missing completely at random (MCAR); i.e., missingness is independent of all other information whether it was collected or not. A sensitivity analysis based on multiple imputation, as described above, may be done in which FCS logistic regression would be the imputation method.

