#### 12.6.4.3 Pregnancy

#### All pregnancy results will be listed.

### 12.6.4.4 Stanford Sleepiness Scale (SSS)

A summary of SSS will show frequency and percentage of subjects at each rating level, and a plot showing mean (SE) SSS at each applicable study time point will be provided.

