### 12.6.4.5 Columbia-Suicide Severity Rating Scale (C-SSRS)

For the 5 suicidal ideation questions ("Wish to be dead," "Non-specific active suicidal thoughts," "Active suicidal ideation with any methods (not plan) without intent to act," "Active suicidal ideation with some intent to act, without specific plan," "Active suicidal ideation with specific plan and intent") and the 5 suicidal behavior questions ("Preparatory acts or behavior," "Aborted attempt," "Interrupted attempt," "Suicide attempt," "Suicide behavior") of the C-SSRS, the number of subjects who answered "yes" will be tabulated for each applicable study time point. Other data collected on the C-SSRS (e.g., ideation intensity measures) will be provided in data listings only.

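### SAP 12.0 divides every categorical percentage by the number exposed, so by-visit rates fall as assessments go missing and differences between arms can be distorted in either direction

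*SAP*

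**What the plan says.** SAP 12.0 covers all categorical variables in two sentences: "Categorical data will be summarized with frequencies and percentages" and "Percentages by categories will be based on the number of subjects exposed within a treatment". The sentence on continuous variables in the same section allows for exceptions and lists the number of observations among its statistics. The categorical rule does neither.

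The rule reaches several tables of values measured at a visit:

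- **Response, remission and CGI-I.** Protocol 9.5.8.4 states: "The categorical outcomes of HAMD17 response, HAMD17 remission, and CGI-I will be summarized by visit". SAP 12.5 adds that "summary tables will show frequencies and percentages of subjects in each category as well as adjusted event rates with SEs", the adjusted rates coming from a GEE model. These are mITT tables (SAP 12.5 and Appendix 3).
- **Sleepiness.** SAP 12.6.4.4: "A summary of SSS will show frequency and percentage of subjects at each rating level". SAP 12.6 places SSS among the variables summarized at each time point.
- **Suicidality.** SAP 12.6.4.5 plans the number of women answering yes, which "will be tabulated for each applicable study time point". It names no percentage and no denominator.

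SAP 8.3 says that unrecorded values count as missing in summaries unless noted otherwise. SAP 9.0 admits a woman to mITT on a single post-randomization efficacy assessment, so mITT women can be missing at later visits.

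**The concern.** A denominator of all women exposed suits events collected throughout follow-up, such as adverse events. It does not suit a value that exists only if the woman was assessed at that visit. A woman not assessed stays in the denominator and cannot enter any numerator.

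For response and remission this amounts to counting missing as failure, a recognised convention that the SAP never declares. The GEE rate beside it is built from recorded values, so the table shows two rates with different missing-data handling and no label. For CGI-I and SSS, the category percentages sum to less than 100%. SSS has no model-based rate to set against them.

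The raw percentages carry weight because SAP 12.0 calls the analysis primarily descriptive and SAP 12.5 offers the modelling only as an aid to interpretation. The arms are small, so one or two absences move a percentage visibly. Cohort 6 is the most exposed, with outpatient visits out to Day 71.

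**Working it through.** The plan states no response rate, drop-out rate or power calculation for a proportion, so there is no figure of its own to reproduce. The check is arithmetic on the rule.

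**Inputs from the documents.** Cohorts of about 10 to 30 women randomized 1:1 (SAP 6.1) give about 5 to 15 per arm. Cohort 3 was recommended to finish at 20 (Protocol 1.2.1.4), about 10 per arm. **Assumed for illustration:** the rates, the counts, and a missing share of 0 to 30% per arm.

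**Formula.** Let x women have the outcome, n be assessed at the visit and N be exposed, with missing share m = 1 − n/N.

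- Rate among women assessed: p = x/n
- Printed rate: x/N = (x/n)(n/N) = p(1 − m)
- Printed difference: p_G(1 − m_G) − p_P(1 − m_P), where G is ganaxolone and P is placebo

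**Equal missingness**, 60% against 30% among women assessed:

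| m in both arms | Printed rates | Difference | Ratio |
|---|---|---|---|
| 0% | 60% vs 30% | 30 points | 2.0 |
| 10% | 54% vs 27% | 27 points | 2.0 |
| 20% | 48% vs 24% | 24 points | 2.0 |
| 30% | 42% vs 21% | 21 points | 2.0 |

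The absolute difference shrinks and the ratio does not change.

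**Unequal missingness:**

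| Rates among assessed | m_G, m_P | Printed rates | Printed difference |
|---|---|---|---|
| 60% vs 30% | 30%, 10% | 42% vs 27% | 15 points (30 among assessed) |
| 60% vs 30% | 10%, 30% | 54% vs 21% | 33 points (30 among assessed) |
| 60% vs 30% | 0%, 30% | 60% vs 21% | 39 points (30 among assessed) |
| 30% vs 30% | 30%, 0% | 21% vs 30% | −9 points (0 among assessed) |

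**Whole-number cases at the trial's arm sizes** (ganaxolone first):

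- 10 exposed per arm, 3 missing on placebo only: 5/10 vs 3/7 is 50.0% vs 42.9%, a difference of 7.1 points. Printed: 5/10 vs 3/10, 20.0 points.
- 10 exposed per arm, 3 missing on ganaxolone only: 4/7 vs 4/10 is 57.1% vs 40.0%, a difference of 17.1 points. Printed: 4/10 vs 4/10, 0 points.
- 15 exposed per arm, 3 and 1 missing: 6/12 vs 6/14 is 50.0% vs 42.9%. Printed: 6/15 vs 6/15, 40% in each arm.

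In the last case the ganaxolone CGI-I or SSS levels at that visit would sum to 12/15 = 80%.

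**Consistency with the rest of the SAP.** SAP 8.3 leaves an unrecorded value out of summaries, while SAP 12.0 keeps the woman in the denominator. The efficacy tables use mITT, which is not the exposed set. SAP 9.0 also groups mITT by assigned treatment and the Safety Set by treatment received, so the SAP 12.0 denominator need not match the arms of the table it appears in.

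**The case against.** The strongest reply is that little is lost. The primary endpoint is a continuous change score, and response, remission and CGI-I are secondary in an unpowered, descriptive Phase 2A study. Frequencies are printed beside the percentages, listings support every table, and the by-visit HAMD17 and SSS summaries give the number of observations. A careful reader could rebuild the rate. The first post-dose efficacy assessment falls while the woman is an inpatient (+12h in Cohorts 1-5, +6h in Cohort 6), so mITT and the exposed set should nearly coincide. In Cohorts 1-5 assessments stay inpatient to +72h, so the effect falls mainly on follow-up visits. All of this stands, and it limits the consequences. It does not make the denominator right or remove the conflict with SAP 8.3.

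Four stronger readings are tempting, and the documents do not support them:

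- **That suicidal-ideation rates will be understated.** SAP 12.6.4.5 plans counts. A percentage would arise only from the general rule in SAP 12.0. The gap there is that no number assessed is given beside the count.
- **That an unassessed woman is recorded as alert.** She falls in no SSS level, including level 1, and the shortfall from 100% is visible.
- **That the rule always hides differences.** It can also inflate or create one, as shown above.
- **That the rate among women assessed is the true rate.** It is unbiased only if missingness is unrelated to outcome, and SAP 12.5 itself allows that women who do worse may miss more assessments. For response, counting missing as failure can then be the more cautious figure, but it should be declared.

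**Conclusion.** The point holds. It is a stated rule that is wrong for by-visit tables, and not merely an omitted detail. Followed literally, it scales each by-visit percentage for response, remission, CGI-I and SSS levels by one minus the share missing at that visit. Equal missingness shrinks the absolute difference; unequal missingness can move it either way.

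The size in this trial cannot be stated, because the documents give no missing-data rate. The figures above rest on assumed counts and rates, and the GEE rates that would stand beside them were not computed. The primary endpoint and the adverse event tables are unaffected. The sponsor should correct the rule before the tables are produced.

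**What to change.** Replace the single denominator sentence in SAP 12.0 with a rule by type of table:

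- **Subject-level Safety Set tables** (adverse events, medications, medical history): keep the number exposed.
- **Disposition:** use the number randomized. Appendix 3 puts Table 14.1.1 on the Randomized Set, and women randomized but never dosed would otherwise be missing from the denominator.
- **By-visit categorical tables** (response, remission, CGI-I, SSS): use the women in that table's analysis set with a non-missing value at the visit. Print that n and add a missing row.
- **C-SSRS:** print the number assessed beside each count.

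If missing-as-non-responder is wanted for response and remission, define it in SAP 12.5 as a separate, labelled analysis beside the observed-case rate. Each then carries its own stated assumption about the missing women.

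The cost is a short SAP amendment and revised table shells. No new data are needed. Any tables already run for Cohorts 1-3 under SAP 10.2 would need to be rerun to the same shells.

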# 12.1 Subject Disposition

The summary of subject disposition will include number and percentage of subjects in each analysis set, subject status at the end of the trial (completed or discontinued), and reason for discontinuation.

# 12.2 Important Protocol Deviations

Per PRA processes, protocol deviations will be entered into our Clinical Trials Management System (CTMS). The study team and the sponsor will conduct on-going reviews of the deviation data from CTMS

and the resulting set of evaluable subjects throughout the study, adjusting the deviation criteria as seems appropriate. The Per Protocol set must be finalized at the post-freeze data review meeting (or earlier), prior to database lock.

Protocol deviations (see definition in Section 8) for subjects in the Safety Set will be summarized by category. Examples of categories that may be used are inclusion criteria, exclusion criteria, study drug, safety assessment, lab/endpoint data, visit window, informed consent, prohibited medication, overdose/misuse, and other.

#### 12.3 Treatments

#### 12.3.1 Extent of Study Drug Exposure

#### 12.3.1.1 IV Only Cohorts

For each IV only cohort, duration of IV exposure (hours), total dose (mg), and mean daily dose (mg) will be summarized for the Safety set, calculated as follows:

#### Duration of Exposure = $\sum t_v + \sum t_b - \sum t_i$ where:

 $t_v$  = all IV/infusion administration time intervals, calculated as end date/time – start date/time (hrs)

 $t_b$  = all bolus administration time intervals, calculated as end date/time – start date/time (hrs)

 $t_i$  = all IV/infusion interruption time intervals, calculated as stop time – start time (hrs). Note:  $\sum t_i$  = Total Duration of Interruptions

Note: Since interruption start/end times but not start/end dates are collected, if end time > start time, it will be assumed that start date = end date; otherwise, it will be assumed that end date = start date + 1.

#### Total Dose = $\sum (t_v r_v c) + \sum v_b c - \sum (t_i r_i c)$ where:

 $t_v$  and  $t_i$  are as defined above (hr)

 $r_v$  = infusion rate (mL/h)

 $r_i$  = infusion rate at start of interruption (mL/h) Note: since neither infusion rate nor date at start of interruption is collected, it will be assumed that  $r_i$  is the same as infusion rate at end of interruption (which is collected), unless otherwise instructed by Sponsor.

c = concentration (mg/mL) Note: Concentration for subjects treated with ganaxolone is cohort-dependent. Concentration for placebo subjects is 0.

 $v_b$  = volume of bolus injected (mL)

Mean Daily Dose =  $\frac{\text{Total Dose}}{\text{Overall Days Exposed}}$  where:

Overall Days Exposed = last end date of last IV/infusion or bolus administration – first start date of first IV/infusion or bolus administration + 1.

Details of infusion interruptions and early discontinuations will be listed.

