## 6.2.4 **Dose Adjustments**

Sedation and dizziness are known effects of ganaxolone at higher doses. If a subject experiences excessive sedation or dizziness the investigator may adjust the dosing by stopping the infusion for a minimum of 1 hour or until the effects resolve and then restarting the dosing at half the rate prescribed for the cohort (for Cohorts 1-5). For example, if the rate prescribed for the cohort is 4 mg/h (16 ml/h), the investigator may stop the infusion for 1 hour and then restart the infusion at 2 mg/h (8 ml/h). If the dose is adjusted, this must be recorded in the source documentation and eCRF. Under these circumstances the subject must be monitored closely for recurrence of sedation.

If the subject experiences excessive sedation or dizziness during the administration of the bolus dose, the dosing should be stopped immediately. The investigator should wait for a minimum of 1 hour or until the effects resolve and then starting the infusion at the rate prescribed for the cohort. Under these circumstances the subject must be monitored closely for recurrence of sedation. The dose of the oral medication in Cohort 6 may be adjusted by lowering the dose from 900 mg to 675 mg or 450 mg, or matching placebo at dinner time if the subject experiences adverse effects, such as sedation in the morning. If the dose is adjusted, this must be recorded in the eCRF. Other dosing adjustments may be possible, but they should be discussed with the medical monitor.

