# 6.5 Drug Administration

# 6.5.1 Administration of IV IP (Cohorts 1-6)

The IP will be administered IV via an indwelling catheter inserted in a vein on the arm or hand. The IP should be given as continuous infusion as instructed. If the study drug is stopped temporarily (e.g. catheter change) the infusion may be re-started at the same rate as before. A new infusion bag should be prepared every 24 hours. The catheter should be flushed with saline at the same time when the tubing is changed. The catheter site should be inspected for inflammation at least twice a day. For details please see pharmacy manual.

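### In Cohorts 1-5 the SAP values an infusion pause at the restart rate, so a half-rate restart after sedation before +48 h can overstate total dose

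*SAP*

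**What the plan says.** SAP Section 12.3.1.1 defines total dose in the IV only cohorts as infused dose plus bolus dose minus the dose not given during interruptions. The last term is interruption time × rate at the start of the interruption × concentration. On that rate the SAP states "since neither infusion rate nor date at start of interruption is collected, it will be assumed that" it equals the "infusion rate at end of interruption (which is collected), unless otherwise instructed by Sponsor".

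Protocol Section 6.2.4 covers excessive sedation or dizziness in Cohorts 1-5. The investigator may pause dosing for at least an hour, or for as long as the symptoms last. The restart is described as "restarting the dosing at half the rate prescribed for the cohort". Protocol Section 6.5.1 covers technical stops such as a catheter change, after which "the infusion may be re-started at the same rate as before".

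Mean daily dose is total dose divided by inclusive calendar dates: "last end date of last IV/infusion or bolus administration – first start date of first IV/infusion or bolus administration + 1". SAP Section 12.3.1.2 (Cohort 6) uses the rate at the start of the interruption with no substitute, and takes interruption times with dates.

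**The concern.** The substitution assumes that the rate is the same on both sides of a pause. The protocol makes that true for a catheter change and false for a pause managed by a half-rate restart. The error is therefore not spread at random. It falls on women paused for sedation or dizziness, which the protocol names as known effects at higher doses, and where it arises it makes their dose look larger than it was. The study's stated purpose is to identify a dose and exposure level that is safe and well tolerated, so the exposure table should be right for these women in particular.

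**Working it through.** **Inputs.** Cohort regimens (Protocol 3.1): 4, 8 or 12 mg/h for 48 h, then half rate for 12 h, with a 12 mg bolus in Cohort 3. The cap for Cohorts 4-5 is 16 mg/h with a 16 mg bolus. Formulas are from SAP 12.3.1.1. Assumptions not in the documents: a pause starting at +8 h, half rate kept from restart to +60 h, and a 9 am start.

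**1. No pause.** The documents state no total dose to reproduce. The rate conversions check (for example 24 mL/h × 0.5 mg/mL = 12 mg/h), and the SAP formula returns the planned totals:
- Cohort 1: 4×48 + 2×12 = 216 mg
- Cohort 2: 8×48 + 4×12 = 432 mg
- Cohort 3: 12 + 12×48 + 6×12 = 660 mg

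**2. A 4-h sedation pause at +8 h in Cohort 3, inside the old-rate record.**
- Delivered: 12 + 12×8 + 6×48 = 396 mg
- SAP: 12 + 12×12 + 6×48 − 4×6 = 420 mg
- Difference: +24 mg, and 24/396 = 6.1%

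In general, with prescribed rate r and a pause of p hours, the error is (r − r/2) × p = (r/2) × p.

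| Regimen | Error per paused hour | 4-h pause at +8 h: SAP vs delivered |
|---|---|---|
| Cohort 1 | 2 mg | 136 vs 128 mg (+6.3%) |
| Cohort 2 | 4 mg | 272 vs 256 mg (+6.3%) |
| Cohort 3 | 6 mg | 420 vs 396 mg (+6.1%) |
| 16 mg/h cap | 8 mg | 560 vs 528 mg (+6.1%) |

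In Cohort 3 a 1-h pause at +8 h gives 420 vs 414 mg (+1.4%), and a 12-h pause gives 420 vs 348 mg (+20.7%). Moving the 4-h pause from a start at 0 h to a start at +44 h changes the delivered dose from 348 to 612 mg, so the error runs from 6.9% to 3.9%.

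**3. Where the error is zero (Cohort 3, 1-h pause).**
- Same-rate restart: 648 vs 648 mg.
- Sedation pause after +48 h, when the rate is already half: 654 vs 654 mg.

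**4. Dependence on how records are cut.** The SAP does not say whether an administration interval runs through a pause. For the 4-h pause in step 2:
- Pause inside the old-rate record: 420 mg (+6.1%).
- Pause inside the new half-rate record: 12 + 12×8 + 6×52 − 4×6 = 396 mg (exact).
- Records already exclude the pause: 396 − 24 = 372 mg (−6.1%).

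**5. Mean daily dose.** A morning start and a stop at +60 h on the evening of Day 3 touch three dates. Per calendar day against per 24 h this gives 72 vs 86.4, 144 vs 172.8 and 220 vs 264 mg in Cohorts 1-3. The ratio is 2.5/3 throughout, one-sixth lower. Early stops behave differently. In Cohort 3, stopping at 14 h gives 12 + 12×14 = 180 mg on one date, or 180 mg/day. Stopping at 16 h gives 204 mg on two dates, or 102 mg/day. Per 24 h these are 308.6 and 306 mg.

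**The case against.** The strongest reply is that little rests on this. The protocol reports no dose adjustment in Cohort 1, in 12 Cohort 2 subjects or in 13 Cohort 3 subjects. With Cohort 3 planned at 20, about seven women remain, roughly half of them on placebo with a dose of zero, plus any in the optional Cohorts 4-5. Interruptions are listed, exposure hours net of pauses do not use the rate, and adverse events leading to interruption or dose reduction are tabulated. No specified efficacy or safety analysis uses these doses, and outputs for the Data Review Committee are specified elsewhere. The sponsor may also override the substitution. All of this stands and sets the severity. It does not make the stated rule correct, and an unspecified override is no substitute for a rule.

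A reader might infer that total dose is misstated generally. It is not: the formula is exact without a pause, after a same-rate restart and after the step-down.

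A reader might also call mean daily dose an arithmetic error. The documents do not support that. The calendar-day denominator is openly defined, Cohort 6 uses the same convention, and for completed infusions ratios between cohorts are preserved. A four-date count (660/4 = 165 mg in Cohort 3) needs an afternoon start or an infusion extended past +60 h, whereas the protocol schedules a morning start and an end on Day 3. What remains is the uneven effect on early stops.

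**Conclusion.** The point holds in a limited form and is minor. For Cohorts 1-5 the substitution contradicts the SAP's own definition of the rate it needs, and the protocol's half-rate restart makes it wrong for sedation or dizziness pauses before +48 h. If the pause lies in an old-rate record, total dose is overstated by half the prescribed rate per paused hour, about 6% for the assumed 4-h pause at +8 h. The SAP leaves record boundaries undefined, so under other layouts the error could be zero or negative; the boundaries need stating for that reason too. The effect is confined to descriptive exposure summaries for the remaining Cohort 3 subjects and any in Cohorts 4-5. Mean daily dose needs a label rather than a correction. No view is taken on the clinical restart rule.

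**What to change.** In SAP Section 12.3.1.1:

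1. Set the interruption rate to the rate in the administration record in force immediately before the pause. Infusion rate is already an input to the formula. Do not use the cohort's scheduled rate: for a second pause after a half-rate restart in Cohort 3 it would be 12 mg/h when 6 mg/h was running.
2. State that the pre-pause record runs through to the restart, so that the pause is subtracted once. With both changes the step 2 example becomes 12 + 12×12 + 6×48 − 4×12 = 396 mg. A pause from 47.5 to 48.5 h is also exact: 12 + 12×48.5 + 6×11.5 − 12 = 651 mg, equal to the 12 + 12×47.5 + 6×11.5 delivered.
3. Flag pauses that cannot be matched to a record. Interruption dates are not collected, and in a 60-h infusion a clock time recurs on two or three dates.
4. Label mean daily dose as per calendar day. Optionally add dose per 24 h of elapsed infusion time, first start to last end, shown beside the hours because it is unstable for very short infusions. Do not divide by duration net of pauses, which raises the figure for paused women: 396/(56/24) = 169.7 mg against 396/2.5 = 158.4 mg.

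The cost is a few SAP lines and some matching in programming, with no new data collection. SAP Section 3.0 allows amendment up to unblinding.
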